# 3.2.2 Caregiver eligibility criteria

Inclusion Criteria	18 years of age or older	
	Family member or friend of an eligible patient	
	Primary person involved in patient's care and best able to participate in the study, as assessed by patient	
Exclusion Criteria	Does not speak English	
	No phone for additional study contacts and follow-up interviews	
	Unable to complete the baseline interview	

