#### 4.3 Secondary Patient and Caregiver Outcomes

We will additionally measure ACP discussions with caregivers, ACP discussions with clinicians, and AD completion (using both a single question and by reviewing medical records for any new ACP documentation). For patients who die during the study period, we chose caregiver-reported measures of goal-concordant EOL care because these validated measures capture overall receipt of goal-concordant care in the last month of life and incorporate the perspectives of bereaved family members. In contrast, measuring receipt of goal-concordant EOL care based on chart review does not account for frequently-encountered situations in which documented ADs do not reflect the

current, real-time clinical scenario. Similarly, we chose a validated, caregiver-reported measure of quality of EOL care because cancer caregivers provide an important and reliable perspective on this outcome. We include measures of caregiver depression, anxiety, and post-traumatic stress symptoms because many patients cite easing the burden on families as a motivator of ACP and it is possible that family caregivers may experience less distress after participating in a facilitated ACP intervention.

	/ Caregiver Outcomes (Aim 1)	II - ·
Specific Measure	Description	Timing
ACP Engagement (primary outcome)	15-item ACP engagement survey assessing ACP processes related to choosing a medical decision maker, discussing and documenting preference for care at EOL, flexibility for surrogate decision making, and asking questions of medical providers. Single summary score (range 0-5 with higher scores indicating higher engagement) has high internal consistency (Cronbach's alpha=0.92) and responsiveness to change. 	Baseline, 12 weeks
ACP discussions with caregivers	"Have you talked with your family or friends about the kind of medical care you would want if you were very sick or near the end of life?" 27, 30, 31	Baseline, 12 weeks
ACP discussions with physicians	"Have you talked with your doctor about the kind of medical care you would want if you were very sick or near the end of life?" 27, 30, 31	Baseline, 12 weeks
AD completion	Single question will assess AD completion. We will additionally assess documented care goals by reviewing medical records for any new ACP documentation, including AD forms or documented discussion.	Baseline, 12 weeks

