Receipt of goal- concordant EOL care	Two validated caregiver-reported questions have been used to measure receipt of goal-concordant EOL care for patients with cancer: (1) "In your opinion, to what extent were [the patient's] wishes followed in the medical care received in the last month of life?"; and (2) Caregivers asked about patient's preferred and actual places of death, with questions separated in the survey to minimize conscious comparison. 	Bereavement
Quality of EOL care	The Caregiver Evaluation of Quality of End-of-Life Care (CEQUEL) scale is a 13- item instrument (range of scores 13-26) with demonstrated reliability and convergent validity among cancer caregivers. Strengths include brevity and clinical relevance, with inclusion of 4 distinct but related factors (prolongation of death, perceived suffering, shared decision-making, and preparation for death) associated with caregiver bereavement outcomes. 	Bereavement

Depression and anxiety symptoms	Hospital Anxiety and Depression Scale (HADS) is a widely-used 14-item instrument measuring symptoms of depression and anxiety. $^{33}$ It has been extensively validated for screening emotional distress among advanced cancer patients $^{34}$ and family members. $^{35}$ Score of $\geq$ 8 on either domain indicate significant symptoms of depression or anxiety with good sensitivity and specificity. $^{36}$	Baseline, 12 weeks, Bereavement
Post-traumatic stress symptoms	Impact of Events Scale is a 22-item self-report instrument for PTSD symptoms with 3 subscales measuring intrusion (8 items), avoidance (8 items) and hyperarousal (6 items). Subscales have high internal consistency (Cronbach's alpha ranging from 0.79-0.92). A score of 30 or higher is considered a clinically significant burden.	Bereavement

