# 5.2 Primary and Secondary Outcomes

All analyses for treatment group comparisons will use an intention-to-treat approach.

The primary outcome is ACP engagement. We will test the effect of treatment assignment on the primary outcome using linear mixed models. The model will include treatment group, and baseline ACP engagement as fixed effects. To adjust for possible clustering of patients seen by the same facilitator or provider, we will include random effects for facilitators (for patients in the facilitated ACP group only) and oncologists.

The same analytic approach will be used for secondary outcomes: perceived quality of EOL care and caregiver symptoms of anxiety, depression and PTSD. Binary outcomes such as ACP discussions, AD completion, documented care goals, and receipt of goal-concordant EOL care will be compared using mixed effect logistic regression with the same set of fixed effects and random effects as in the models for continuous outcomes. We will also compare the rates of completion of intervention between the two intervention groups, using the same model as for other binary outcomes.

Analyses of health care utilization data will use GLMM (generalized linear mixed model), with logit link (binary distribution) for dichotomous (yes/no) health care outcomes such as chemotherapy within last 2 weeks of life. Again, we will use intervention group and baseline ACP as fixed effects and oncologist and clinic as random factors.

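### The bereaved-caregiver PTSD model adjusts only for the patient's baseline ACP engagement; adding the caregiver's own baseline HADS could gain precision from data already scheduled

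*Combined protocol and SAP*

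**What the plan says.** **Outcome.** The table in section 4.3 defines the PTSD measure: "Impact of Events Scale is a 22-item self-report instrument for PTSD symptoms with 3 subscales measuring intrusion (8 items), avoidance (8 items". Its row ends "clinically significant burden. Bereavement", so bereavement is its only time point.

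**Available baseline.** The same table lists a second caregiver distress measure: "Hospital Anxiety and Depression Scale (HADS) is a widely-used 14-item instrument measuring symptoms of depression and anxiety". Its timing is "Baseline, 12 weeks, Bereavement". The text of 4.3 makes clear that caregivers are assessed: "We include measures of caregiver depression, anxiety, and post-traumatic stress symptoms because many patients cite easing the burden on families as a motivator". Section 3.2.2 excludes a caregiver who is "Unable to complete the baseline interview", and section 3.6 randomizes pairs only after the baseline interviews. Caregiver HADS is therefore a pre-randomization measure.

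**Model.** Section 5.2 says of the primary outcome: "The model will include treatment group, and baseline ACP engagement as fixed effects". Random effects for oncologist and, in the facilitated arm, facilitator are added. The same approach is then extended to "perceived quality of EOL care and caregiver symptoms of anxiety, depression and PTSD". No caregiver baseline covariate is named.

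**Power.** Section 5.5 gives an effective caregiver sample of 254, with 83.2% power at d=0.368 for caregiver anxiety and depression and 97.6% for a moderate effect on quality of EOL care. It describes power as similarly adequate for all caregiver-reported outcomes and gives no separate figure for PTSD.

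**The concern.** ACP engagement is the patient's report of planning behaviour. It comes from a different person and measures a different construct from a caregiver's later post-traumatic stress, so there is little reason to expect it to explain much variance in that outcome. The caregiver's own anxiety and depression before randomization are a more natural predictor, and they are already being collected.

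Two readings of 5.2 are possible. Taken literally, every secondary model carries baseline ACP engagement. Taken charitably, each outcome is adjusted for its own baseline. The literal reading fits better, because 5.2 goes on to specify the same set of fixed effects for the binary outcomes and baseline ACP for the utilization outcomes. The choice does not matter here: PTSD has no baseline of its own, so neither reading puts a caregiver covariate into its model.

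At stake is the width of the confidence interval for one secondary outcome, and how far a chance imbalance in caregivers' prior distress feeds into its estimate.

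**Working it through.** **Inputs from the documents.** 400 patients; 75% caregiver participation; 15% loss to follow-up; effective caregiver sample 254; α=0.05 with two-sample t-tests; d=0.368; 90% of patients expected to die (all section 5.5); 1:1 allocation (section 3.6).

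**Assumptions.** The test is two-sided; 5.5 does not state sidedness. The correlation r between baseline HADS (both scores together) and the bereavement Impact of Events score is not in the documents, so it is varied from 0.1 to 0.5. Baseline ACP engagement is taken to explain essentially none of that score. No design effect is applied, because 5.5 gives no values for the cluster size, its coefficient of variation or the intracluster correlation.

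**Step 1: reproduce the plan.** 400 × 0.75 × 0.85 = 255, against 254 stated. With 127 per arm, the noncentral t calculation gives 83.2% at d=0.368 (stated 83.2%) and 97.8% at d=0.5 (stated 97.6%). The plan's caregiver figures therefore reproduce as unadjusted comparisons without a design effect.

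**Step 2: add the covariate.** Adjustment multiplies the residual variance by (1 − r²). The standardized effect becomes d/√(1 − r²), and the equivalent unadjusted sample is N/(1 − r²). For example, at r=0.3: 0.368/√0.91 = 0.386, and 254/0.91 = 279.

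**Step 3: apply the death rate.** The scale can be completed only after the patient has died, and 254 does not include the 90% figure. 400 × 0.75 × 0.85 × 0.90 = 229.5, taken as 229.

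| r | Residual variance | Power, N=254 | Equivalent N | Power, N=229 | Equivalent N |
|---|---|---|---|---|---|
| 0 | 1.00 | 83.2% | 254 | 79.2% | 229 |
| 0.1 | 0.99 | 83.5% | 257 | 79.6% | 231 |
| 0.2 | 0.96 | 84.7% | 265 | 80.8% | 239 |
| 0.3 | 0.91 | 86.5% | 279 | 82.8% | 252 |
| 0.5 | 0.75 | 92.1% | 339 | 89.3% | 305 |

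The effect detectable with 80% power falls from 0.353 (r=0) to 0.337 (r=0.3) or 0.306 (r=0.5) at N=254. At N=229 it falls from 0.372 to 0.355 or 0.322. Losing two degrees of freedom changes none of these figures at the precision shown.

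The d of 0.368 is only a yardstick. Section 5.5 supports it with a study of the HADS, and nothing in the documents makes it a relevant difference on the Impact of Events Scale.

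**The case against.** The strongest reply is that nothing here is wrong. Pairs are randomized after baseline, so leaving out a prognostic covariate does not bias the treatment comparison. The gain also rests on a correlation the documents do not supply. HADS, like ACP engagement, is a different construct from post-traumatic stress, and it may be measured long before the death. At r=0.1 the gain is negligible and at r=0.2 it is about 1.5 percentage points. At the plan's own 254, power at the yardstick effect is above 80% without adjustment.

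All of this stands. It limits the size of the point but does not remove it: a gain in precision from data already scheduled is worth naming in advance even if it turns out modest.

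A reader might infer several stronger claims, which the documents do not support:

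- **Every caregiver will have a usable baseline HADS.** Completing the baseline interview is required, but section 6.2 lets participants skip questions. Some scores may be missing, and fitting complete cases only would give back part of the gain.
- **PTSD is uniquely exposed.** CEQUEL, goal-concordant care and the bereavement HADS come from the same bereaved caregivers.
- **The trial is underpowered for PTSD.** Power falls below 80% at the yardstick effect only if 254 is replaced by 229. Whether 254 should carry the death rate is a separate sample-size question.
- **HADS is left out of the imputation model.** Section 5.3 lists no imputation variables, so its omission cannot be shown.

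**Conclusion.** The point holds as a precision improvement to one secondary outcome. The Impact of Events Scale has no baseline, its planned model carries no caregiver covariate on any reading of 5.2, and a pre-randomization caregiver measure is available. The planned analysis is not biased by this.

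At d=0.368 and N=254 the gain is 0.3 percentage points of power at r=0.1, 3.3 at r=0.3 and 8.9 at r=0.5. At N=229 the corresponding gains are 0.4, 3.6 and 10.1 points. These figures rest on an assumed correlation, a borrowed effect size, a negligible contribution from ACP engagement and no allowance for clustering. The documents cannot show where in this range the trial will fall.

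**What to change.** In section 5.2, state that the Impact of Events model includes the caregiver's baseline HADS anxiety and depression scores as fixed effects, in addition to treatment group and baseline ACP engagement. Add a simple rule for missing baseline HADS, such as single or multiple imputation of the covariate, so that no caregiver with an outcome is dropped.

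Section 5.3 can name the same scores as variables in the imputation model for this outcome. Carrying them into the CEQUEL model is optional; no gain has been estimated there.

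The change should be made before the final analysis so that the covariates are not chosen after seeing results. It costs a few sentences of text and two degrees of freedom, with no new data collection. If the correlation is 0.1 or less, it will gain little.

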#### 4.4 Healthcare Utilization Outcomes

Using methods refined in our previous work, we will assess healthcare utilization at the end of life via caregiver bereavement interviews and medical record review, allowing us to accurately assess use for participants hospitalized in multiple hospital systems. We will measure intensity of EOL care using the American Society of Clinical Oncology's Quality Oncology Practice Initiative (QOPI) and National Quality Forum (NQF)-endorsed measures: chemotherapy administered within the last 2 weeks of life; hospitalizations (>1) or ICU admission in the last month of life; >1 emergency room visit in the last month of life; hospice enrollment; hospice enrollment within 3 days of death; and number of days in hospice.

We will additionally assess ACP implementation costs by tracking staff time spent on each intervention arm. Staff time costs for each intervention will be estimated by multiplying staff training and patient care time related to the intervention in hours by the average hourly wage for US nursing and social work staff of comparable levels.

#### 4.5 In-depth Interviews

We will conduct in-depth interviews with a subset of patients, caregivers, and clinicians to identify contexts and mechanisms that influence ACP effectiveness. These interviews are based on a realist evaluation paradigm, drawing on qualitative methods to investigate factors and conditions under which certain outcomes will or will not be realized. This contextual evaluation expands on the comparative effectiveness data generated in Aims 1 and 2 to answer the guiding questions (1) "what

\_\_\_\_\_

makes each ACP intervention work," and (2) "for whom and under what circumstances is each ACP intervention most effective." 44

Patients and caregivers will be invited to participate in in-depth interviews after completing trial outcome assessments (12-week and bereavement, respectively) to avoid impacting trial integrity. We will recruit equal numbers of participants from each ACP intervention arm. Within each intervention arm, we will include participants for whom the intervention was succesful (defined as an increase in ACP engagement at 12 weeks) and not successful (defined as no increase in ACP engagement at 12 weeks). This sampling strategy will ensure elicitation of a spectrum of experiences regarding what makes each intervention work (or not work) for changing ACP behaviors. We will aim for linked patient-caregiver pairs because caregivers may lend additional perspective on patient EOL experiences. Because ACP also involves clinicians and healthcare systems, we will ask patients to identify a clinician most involved in decisions about their care and interview these stakeholders after patient and caregiver interviews have been completed. As recommended for qualitative research, the sample size is not fixed. Rather, we will conduct interviews until thematic saturation is reached, meaning no new themes emerge from the data. Based on our prior work, we anticipate that this will involve at least 60 patients and 60 caregivers and approximately 60 clinicians. 45-48

Interviews will be conducted using semi-structured interview guides informed by (1) a theoretical framework for ACP based on behavior change theory and (2) the literature on factors that may affect the ability of ACP interventions to improve ACP outcomes. Interview guides will be developed by a multidisciplinary group (including patient and caregiver representatives) and piloted with 2-3 representative stakeholders prior to use. All interviews will be conducted by an experience qualitative researcher with extensive in-depth interviewing experience, audio-recorded, and transcribed verbatim. Interview questions will be modified as new themes emerge from the data.

#### 4.6 Additional Measures

We will collect basic demographic data from participants at time of enrollment, including age, sex, race/ethnicity, religion, social support (8-item modified Medical Outcomes Study Social Support

Survey), health literacy (single-item question validated among diverse patient populations), length of patient relationship with oncologist, cancer type, and performance status. We will additionally assess illness understanding, care preferences, past ACP and decision-making experiences (prior surrogate, prior experiences making decisions for self or others), distress (single-item distress thermometer), and decisional certainty (decisional conflict scale).

As recommended for trials of complex interventions, we will collect process data to understand ACP implementation in both arms. We will track the timing, length, and content of ACP using standardized checklists and website usage data.

#### 5. STATISTICAL ANALYSIS PLAN

#### 5.1 Baseline Data

We will evaluate the statistical properties of baseline and follow-up outcome measures, including potential outliers, normality, and missing data, using summary statistics and graphical tools. Participant demographics and clinical characteristics will be presented as frequency (%) for categorical variables and mean (standard deviation) for continuous variables (or median and range for continuous variables with heavily skewed distributions). Results will be reported following the CONSORT guideline.

# 5.2 Primary and Secondary Outcomes

All analyses for treatment group comparisons will use an intention-to-treat approach.

The primary outcome is ACP engagement. We will test the effect of treatment assignment on the primary outcome using linear mixed models. The model will include treatment group, and baseline ACP engagement as fixed effects. To adjust for possible clustering of patients seen by the same facilitator or provider, we will include random effects for facilitators (for patients in the facilitated ACP group only) and oncologists.

The same analytic approach will be used for secondary outcomes: perceived quality of EOL care and caregiver symptoms of anxiety, depression and PTSD. Binary outcomes such as ACP discussions, AD completion, documented care goals, and receipt of goal-concordant EOL care will be compared using mixed effect logistic regression with the same set of fixed effects and random effects as in the models for continuous outcomes. We will also compare the rates of completion of intervention between the two intervention groups, using the same model as for other binary outcomes.

Analyses of health care utilization data will use GLMM (generalized linear mixed model), with logit link (binary distribution) for dichotomous (yes/no) health care outcomes such as chemotherapy within last 2 weeks of life. Again, we will use intervention group and baseline ACP as fixed effects and oncologist and clinic as random factors.

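### Section 5.2 should state that caregiver HADS, ACP discussions and self-reported AD completion are adjusted for their own pre-randomization baseline as well as for baseline ACP engagement

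*Combined protocol and SAP*

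**What the plan says.** Section 5.2 specifies the primary linear mixed model as follows: "The model will include treatment group, and baseline ACP engagement as fixed effects". Random effects for oncologist, and for facilitator in the facilitated arm, are added.

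The secondary outcomes are then described by reference to that model:

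- Continuous outcomes: "The same analytic approach will be used for secondary outcomes: perceived quality of EOL care and caregiver symptoms of anxiety, depression and PTSD".
- Binary outcomes, expressly including ACP discussions and AD completion: mixed logistic regression "with the same set of fixed effects and random effects as in the models for continuous outcomes".
- Healthcare utilization: "Again, we will use intervention group and baseline ACP as fixed effects".

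No sentence enters a secondary outcome's own baseline.

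The outcome table in section 4.3 shows what is available. HADS is timed "Baseline, 12 weeks, Bereavement". Both discussion items and AD completion are timed at baseline and 12 weeks. AD completion has two sources: "Single question will assess AD completion", and a chart component obtained "by reviewing medical records for any new ACP documentation, including AD forms or documented discussion". Quality of EOL care (CEQUEL), post-traumatic stress and goal-concordant care are measured only at bereavement.

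Section 3.6 randomizes after the baseline interviews. Section 3.2 admits patients who already have an AD.

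**The concern.** A baseline measurement of the same outcome is usually its best single predictor. Here it is collected before allocation, so it is a valid covariate, but the plan does not commit to using it.

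The engagement score is an uneven substitute. It is a patient's report, so it is at most a remote proxy for a caregiver's anxiety or depression. It is closer to the discussion and AD outcomes, because the survey covers "discussing and documenting preference for care at EOL".

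Two things are at stake. One is power: section 5.5 plans 83.2% for caregiver anxiety and depression and more than 78% for ACP discussions, neither with much to spare. The other is prespecification: two analysts could fit different HADS models and both claim to follow section 5.2. That choice should not be open once data have been seen.

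**Working it through.** **Inputs from section 5.5.** Alpha 0.05 (two-sided assumed; the plan does not say). Caregiver outcomes: effective N 254, so 127 per arm, d = 0.368. Patient outcomes: 400 × 0.75 = 300, so 150 per arm. Discussions 25% vs 40%; AD completion 50% vs 70%.

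**1. Reproducing the plan's figures**

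- HADS: noncentrality = 0.368 × √(127/2) = 2.93 on 252 df, power 83.2%. This matches.
- Discussions: pooled SE √(2 × 0.325 × 0.675/150) = 0.0541; unpooled SE √((0.1875 + 0.24)/150) = 0.0534; z = (0.15 − 1.96 × 0.0541)/0.0534 = 0.82; power 79.5%. This agrees with the stated >78%.
- AD completion: pooled SE √(2 × 0.6 × 0.4/150) = 0.0566; unpooled SE √((0.25 + 0.21)/150) = 0.0554; z = (0.20 − 1.96 × 0.0566)/0.0554 = 1.61; power 94.6%. The plan states >99%, which does not reproduce at N = 300.

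**2. Caregiver HADS with a covariate.** A covariate correlated r with the outcome raises the effective d to 0.368/√(1 − r²). This is a t-test calculation without random effects.

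| Covariate | Assumed r | Effective d | Power |
|---|---|---|---|
| Patient engagement | 0 to 0.2 | 0.368 to 0.376 | 83.2% to 84.7% |
| Own baseline | 0.3 | 0.386 | 86.5% |
| Own baseline | 0.5 | 0.425 | 92.1% |
| Own baseline | 0.7 | 0.515 | 98.3% |

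At r = 0.5 the residual variance falls by 25%, so 127 × 0.75 ≈ 95 per arm would give the power that now needs 127. Section 5.5 does not say which HADS time point its figure concerns. The low end of r is more plausible at bereavement.

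**3. ACP discussions.** Simulation with 150 per arm, 4,000 trials per scenario and a Wald test. Overall rates were fixed at the plan's values, with equal persistence in both arms. Engagement was set 0.5 or 1.0 SD higher in patients with a prior discussion, and also predicted the outcome directly (log-odds slope 0, 0.5 or 1.0 per SD).

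| Prior discussion / still yes at 12 weeks | Engagement only | Plus own baseline | Gain (points) |
|---|---|---|---|
| 5% / 70% | – | – | 0.5–2.0 |
| 10% or 20% / 50% | – | – | 0.3–1.6 |
| 10% / 70% | 79.0–87.8% | 81.9–88.8% | 1.0–3.3 |
| 10% / 85% | 79.0–87.7% | 84.5–90.7% | 2.5–5.5 |
| 20% / 70% | 79.5–88.9% | 86.2–91.5% | 2.6–6.6 |
| 20% / 85% | 80.9–88.9% | 92.6–95.6% | 6.7–12.2 |

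The last row is extreme. Prior discussants supply 0.20 × 0.85 = 17 points of each arm's rate, so new discussions would be (25 − 17)/80 = 10% vs (40 − 17)/80 = 29%.

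With random effects (assumed 30 oncologists with ICC 0.05, 4 facilitators with ICC 0.01; 800 trials), engagement-only power is 75–82% and the gain 1–6 points, or 8–11 in the extreme scenario. With 10% of baseline items skipped and a missing indicator, gains are 1.6–5.8 points (8.6–10.3 in the extreme scenario).

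**4. AD completion, same method.** Engagement-only power is about 94–98%. Gains: 0.2–1.1 points (20% prior AD / 85% persistence), 0.5–2.0 (20%/95%), 0.5–2.7 (40%/85%), 1.3–4.3 (40%/95%).

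**5. Separation.** The discussion items ask whether the patient has ever talked, so a baseline yes should rarely revert. With 10% of 300 = 30 baseline-yes patients, the chance that none reverts is 0.95³⁰ = 21% at 95% persistence and 0.98³⁰ = 55% at 98%. If yes never reverts, the comparison rests on baseline-no patients. Simulated power still rises, from 78.6% unadjusted to 89.2% at 10% prior discussion.

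**6. Meaning of the odds ratio.** In the 20%/85% scenario (slope 0, no random effects) the median log odds ratio moves from 0.71 to 1.06 when own baseline is added. The mean standardised risk difference stays at 0.147–0.152 across scenarios with either covariate set.

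**The case against.** The strongest case is that nothing is wrong. In the primary model the covariate is the outcome's own baseline, so the same approach applied to HADS may already mean baseline HADS. CEQUEL and post-traumatic stress, in the same sentence, have no baseline, but that may only mean the term cannot apply to them. The utilization paragraph also concerns outcomes without a baseline, so it does not settle the matter. On that reading the HADS gain is zero and the change is clarification. This stands, and is why the HADS part is put conditionally. It does not reach the binary outcomes, whose fixed effects are tied explicitly to the named set.

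Second, section 5.5 plans secondary power from unadjusted tests, and the HADS and discussion figures reproduce without covariates, so no target is missed. That also stands: this is a gain forgone. Outside HADS it is modest, and for AD small.

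Third, the change has a cost. The discussion models can nearly separate, and a risk difference from a mixed logistic model needs a rule for the random effects. Both points are right and are met in the fix.

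A reader might infer that the plan certainly adjusts caregiver HADS for the wrong person's score, or that the secondary comparisons are biased. The wording leaves the first open. Randomization rules out the second in expectation.

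**Conclusion.** The point holds as an inexpensive improvement to the secondary analyses, plus one ambiguity to close. Section 5.2 commits ACP discussions and AD completion to treatment and baseline engagement only, and leaves the HADS covariate unclear, although each outcome's own baseline is in hand before randomization. The primary outcome and sample size are untouched.

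The benefit is potentially largest for caregiver HADS: about 3 to 15 points for r from 0.3 to 0.7, and nil if own baseline was already meant. It is typically about 1 to 6 points for discussions, more only if prior discussion is common and highly persistent. For self-reported AD completion it is about 0 to 3 points in most scenarios. The documents give none of the correlations, prevalences, persistence values or ICCs behind these sizes.

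The 94–98% for AD completion is a simulated result at N = 300, not the protocol's figure. A reader might put its gap from the stated >99% down to the choice of covariates. The documents do not support that: the unadjusted calculation already gives 94.6%, so that discrepancy is separate.

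**What to change.** Amend section 5.2 before database lock:

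- **Covariates.** State that the models for caregiver HADS anxiety and depression (12 weeks and bereavement), each ACP-discussion item and self-reported AD completion add that outcome's own baseline to treatment group and baseline ACP engagement. Leave the planned random effects unchanged.
- **Exceptions.** Keep baseline ACP engagement alone for outcomes measured only at bereavement, and for newly documented ACP from chart review, which has no matching baseline item.
- **Missing baseline items.** Keep participants who skipped a baseline item in the model through a missing indicator, with the multiple imputation already planned in section 5.3 as a check.
- **Separation.** If no, or almost no, baseline-yes patient reverts, use a named fallback: Firth-penalised logistic regression, or analysis among baseline-no patients.
- **Effect measure.** Because section 5.5 plans in absolute differences, report a standardised risk difference with its confidence interval beside the conditional odds ratio, and state how the random effects are averaged over.

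No new data are needed. Sections 3.2.1 and 3.2.2 exclude anyone unable to complete the baseline interview, so among enrolled participants only skipped items should be missing. The cost is a few more lines of specification and an odds ratio with a conditional meaning.
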